**RO7049389—F. Hoffmann-La Roche Ltd**

29/Protocol YP39406, Version 4

The projected dose levels, which may be adjusted based on the emerging safety, tolerability, and PK data from this study and study YP39364 (entry into human), are shown in [Table 1](#).

**Table 1 Initial Dose of RO7049389 or Placebo**

	Cohort 1	Cohort 2	Cohort 3	Cohort 4 a
SAD	200 mg	400 mg	600 mg	800 mg
MAD	N/A	200 mg q12h b,e	400 mg q12h	600 or 800 mg q24h

- a. Cohort 4 is optional and will be conducted in case that the total daily dose of the estimated efficacious dose from YP39364 is between 400 mg to 600 mg q12h or higher.
- b. The dose of 200 mg q12h in MAD cohort 2 will be optional and will be conducted in case the total daily dose of the estimated efficacious dose from YP39364 is lower than 400 mg q12h.

The rationale for dose selection is described in Section [3.2.1](#).

The highest dose level *and exposure* to be included in this study will be within the dose *and exposure* that has been demonstrated to be safe and well tolerated in FIH Study YP39364.

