##### 3.1.1 Overview of Study Design

This study will leverage the data which will have been generated in the FIH study, allowing targeted evaluation of fewer doses.

Healthy subjects will be enrolled into one of 3 planned cohorts and one optional cohort. Cohort 1 will include 4 healthy subjects, with 2 randomly assigned to RO7049389 and 2 assigned to placebo. From Cohort 2 to Cohort 4, each of the cohorts will include 12 healthy subjects with 10 subjects randomly assigned to RO7049389 and 2 subjects randomly assigned to placebo.

In Cohort 1, subjects will receive one single dose of the assigned study medication. In subsequent cohorts, subjects will receive one single dose of the assigned study medication, followed by a wash-out period of approximately 1-week before entering into a MAD phase of the study. Subjects in the MAD cohorts will be from the SAD cohorts after the wash-out period (see [Figure 1](#)), or from new enrollments if there are discontinuations between the SAD phase and MAD phase for reasons other than safety.

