### **3.1.1.2 MAD Phase**

In Cohorts 2, 3 and 4, after a post-SAD phase wash-out period of at least one week, all subjects will be admitted to a clinical research unit for 16 nights from Day -1 to Day 16 (discharged on Day 16). Subjects will be administered multiple oral doses of either RO7049389 or placebo twice daily (q12h) or once daily (q24h) from Day 1 to Day 14 (the currently planned regimen is q12h, but will be evaluated based on emerging data from Study YP39364). The allocation of RO7049389 or placebo will be the same as that which was administered in the SAD phase. All subjects will return for a follow-up visit on Day 21 ( $\pm 1$ ), and will receive a follow-up call on Day 42.

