#### **4.3.2 Dosage, Administration and Compliance**

##### **4.3.2.1 RO7049389 and Placebo**

The health care professionals at the study site administering the study drug to the subject must check to be sure that the study drug is swallowed.

The qualified pharmacist at the pharmacy will keep drug accountability and record the study drug batch or lot number received by each subject during the study.

Accountability and subject compliance will be assessed by maintaining adequate study drug dispensing records. The Investigator is responsible for ensuring that dosing is administered in compliance with the protocol. Delegation of this task must be clearly documented and approved by the Investigator.

Active or placebo doses will be administered orally to the study subjects with approximately 240 mL of still water at room temperature. An additional amount of water up to 100 mL can be given to assist dose administration only if needed. The dose in mg, the date and time of dosing, and the exact volume of water should be recorded on the eCRF (the exact volume of water consumed during dose administration will be recorded during the in-clinic period).

The qualified individual responsible for dispensing the study drug will prepare the correct dose according to the randomization schedule. This individual will write the date dispensed and study subject's number and initials on the study drug vial label and on the Drug Accountability Record. This individual will also record the study drug batch or lot number received by each study subject during the study.

Guidelines for dosage modification and treatment interruption or discontinuation are provided in Section 3.1.2.

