#### **MAD Phase**

RO7049389 or matching-placebo will be administered orally with 240 mL of water to the healthy subjects by investigational staff from Day 1 through to Day 13 q12h, and on Day 14 once in the morning.

*Except for cohort 4, which will be in the fasted state,* a standard breakfast or dinner will be served to healthy volunteers 30 minutes prior to dosing, which should be consumed within 30 minutes. RO7049389 or placebo will then be administered.

Lunch will be served approximately 4-5 hours post-morning-dose. The second daily dose will be administered in the evening, approximately 12 hours after the morning dose.

Timing of meals relative to dosing may be changed according to emerging data.

Guidelines for dietary stipulations are provided in Section 4.4.3 and Section 4.4.4.

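### Cohort 4 multiple dosing: Table 1 sets one dose a day, but the administration instruction in Section 4.3.2.1 sets two

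*Combined protocol and SAP*

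**What the plan says.** Three places in the current protocol text (Version 4) bear on how often Cohort 4 is dosed in the multiple-dose phase.

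- **Table 1 (Section 3.1.1)** assigns Cohort 4 "600 or 800 mg q24h". Cohort 4 is optional. The text introducing the table calls its dose levels projected, "which may be adjusted based on the emerging safety, tolerability, and PK data from this study and study YP39364".
- **Section 4.3.2.1, MAD Phase**, says that drug or placebo is given "from Day 1 through to Day 13 q12h, and on Day 14 once in the morning". It adds: "The second daily dose will be administered in the evening, approximately 12 hours after the morning dose". Its only provision specific to this cohort concerns food: "Except for cohort 4, which will be in the fasted state".
- **Section 3.1.1.2** covers Cohorts 2, 3 and 4 together. It provides for dosing "twice daily (q12h) or once daily (q24h) from Day 1 to Day 14 (the currently planned regimen is q12h", with that plan open to re-evaluation as data emerge from the first-in-human study. It does not say which cohort would be dosed once daily.

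Section 4.3.2.1 also states: "The Investigator is responsible for ensuring that dosing is administered in compliance with the protocol".

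**The concern.** Section 4.3.2.1 is where the site looks for the administration schedule. It names Cohort 4 and makes an exception for it, but only for meals, so it cannot be read as silently leaving that cohort out of twice-daily dosing. Table 1 says once daily. An investigator bound to dose as the protocol requires therefore has two frequencies to comply with.

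Three things are at stake:

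- **Dose received.** Following Section 4.3.2.1 at the Table 1 unit dose doubles the daily dose on 13 of the 14 days in healthy volunteers, who have no therapeutic benefit to expect.
- **Classification.** Under Section 4.3.2.1 an evening dose in Cohort 4 is compliant. Under Table 1 the same tablet takes the subject above the dose being studied, which is how Section 5.2.5.10 defines an overdose.
- **Pharmacokinetics.** The AUC over a dosing interval, the trough concentration and the accumulation index (Section 3.3.2) all depend on whether the interval is 12 or 24 hours.

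**Working it through.** The plan gives no dose count or total daily dose for Cohort 4 multiple dosing, so there is no stated figure to reproduce. The check counts doses under each text.

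**Inputs**

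- Unit dose 600 or 800 mg, interval 24 h: Table 1.
- Two doses a day on Days 1–13 and one on Day 14: Section 4.3.2.1.
- Dosing period Days 1–14: Section 3.1.1.2.
- Active subjects in Cohort 4: 10, from "12 healthy subjects with 10 subjects randomly assigned to RO7049389" (Section 3.1.1).

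Section 4.3.2.1 states no milligram dose, so the unit dose has to come from Table 1 in both columns.

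**Formulas**

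- Doses under Section 4.3.2.1 = 2 × 13 + 1 = 27
- Doses under Table 1 = 1 × 14 = 14
- Daily dose = unit dose × doses per day
- Cumulative dose = unit dose × number of doses

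| Per subject | Section 4.3.2.1 at Table 1 unit dose | Table 1 |
|---|---|---|
| Doses | 27 | 14 |
| Daily dose, Days 1–13, 600 mg unit | 2 × 600 = 1200 mg | 600 mg |
| Daily dose, Days 1–13, 800 mg unit | 2 × 800 = 1600 mg | 800 mg |
| Daily dose, Day 14 | 600 or 800 mg | 600 or 800 mg |
| Cumulative, 600 mg unit | 27 × 600 = 16,200 mg | 14 × 600 = 8,400 mg |
| Cumulative, 800 mg unit | 27 × 800 = 21,600 mg | 14 × 800 = 11,200 mg |

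**Differences**

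- Extra doses per subject: 27 − 14 = 13, all in the evening.
- Ratio of doses, and so of cumulative dose: 27 / 14 = 1.93.
- Excess cumulative dose: 13 × 600 = 7,800 mg to 13 × 800 = 10,400 mg.
- Across the cohort: 13 × 10 = 130 extra active doses at most, if all 10 active subjects complete.

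**Which text is meant?** Cohort 4 is to be dosed fasted. Under Section 4.3.2.1 lunch comes 4–5 h after the morning dose and the evening dose at about 12 h, so the evening dose would fall 12 − 5 = 7 to 12 − 4 = 8 h after lunch is served. The only fast the protocol defines is at least 8 h overnight, for the single-dose phase (Sections 3.1.1.3 and 4.3.2.1). No fasted evening dose is described. This points to once daily as the intention, and to Section 4.3.2.1 as the text that needs correcting.

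**The case against.** The strongest reply is that neither text, read alone, prescribes 1200–1600 mg a day. Section 4.3.2.1 gives no milligram dose, so a reader must go to Table 1 for it, and there the dose and its once-daily interval share one cell. To reach the doubled dose, someone must take half of that cell and ignore the rest. Table 1 is also the only visible cohort-specific text, and Section 3.1.1.2 expressly permits once-daily dosing.

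Safeguards add to this:

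- Subjects are inpatients and staff give every dose.
- Doses are prepared according to the randomization schedule (Section 4.3.2.1).
- Sponsor and investigator must agree before multiple dosing starts (Section 3.1.2).
- Dose and exposure are capped at what the first-in-human study has shown to be safe.

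Appendices 3 and 4 and Figure 1 could not be consulted, and they may show the right schedule.

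Much of this stands. It makes the doubled dose less likely, and the 130-dose figure is an upper bound for an optional cohort. It does not remove the conflict. The pre-dosing agreement concerns whether the safety data support continuing, not dosing frequency. If the appendices show once daily, Section 4.3.2.1 would still contradict both them and Table 1.

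How the mismatch arose is also uncertain. The visible summary of changes for Section 4.3.2.1 shows the fasted exception and no change of frequency, which suggests a missed follow-on edit. The log is excerpted and part of the rationale is redacted, so this is an inference only.

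**Conclusion.** The point holds. The current text gives Cohort 4 two incompatible dosing frequencies, and no visible section resolves them. Once daily is probably intended, so Section 4.3.2.1 is wrong as written for this cohort.

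The size is a factor of 2 in daily dose on Days 1–13 and 1.93 in cumulative dose. It assumes that Section 4.3.2.1 is followed literally, that Table 1 unit doses are used, and that Cohort 4 runs.

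No breach of the first-in-human dose cap is claimed. The highest multiple dose visible from that study is 400 mg twice daily, i.e. 2 × 400 = 800 mg a day, at the June 2017 data cutoff. Later data are not shown.

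This should be fixed before Cohort 4 multiple dosing opens. The safeguards lower the chance of harm but are no substitute for a correct instruction.

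**What to change.** 1. In Section 4.3.2.1, limit the twice-daily schedule and the evening dose to Cohorts 2 and 3, and add: *Cohort 4: once daily in the morning, fasted, Days 1–14, no evening dose.* This gives 14 doses, 600–800 mg a day, and 8,400–11,200 mg in total.
2. In Section 3.1.1.2, state the planned regimen as q12h for Cohorts 2 and 3 and q24h for Cohort 4.
3. Check that Figure 1 and Appendices 3 and 4 show the same frequency.

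If the sponsor in fact intends twice-daily dosing for Cohort 4, correct Table 1 instead. In that case, confirm that 1200–1600 mg a day and the resulting exposure lie within the first-in-human limit stated below Table 1.

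The cost is wording in two sections and a consistency check, with no added subjects, visits or samples. If the change counts as a substantial amendment, it needs the ethics and regulatory approval described in Section 9.5 before use.

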### **3.1.1.1 SAD Phase**

All subjects will be admitted to a clinical research unit for 3 nights from Day -1 through Day 2, and discharged on Day 3. On Day 1, subjects will be administered a single dose of either RO7049389 or placebo. Subjects who will not enter the MAD phase (Cohort 1) will return for a follow-up visit on Day 8 ( $\pm 1$ ), and will receive a follow-up call on Day 29.

### **3.1.1.2 MAD Phase**

In Cohorts 2, 3 and 4, after a post-SAD phase wash-out period of at least one week, all subjects will be admitted to a clinical research unit for 16 nights from Day -1 to Day 16 (discharged on Day 16). Subjects will be administered multiple oral doses of either RO7049389 or placebo twice daily (q12h) or once daily (q24h) from Day 1 to Day 14 (the currently planned regimen is q12h, but will be evaluated based on emerging data from Study YP39364). The allocation of RO7049389 or placebo will be the same as that which was administered in the SAD phase. All subjects will return for a follow-up visit on Day 21 ( $\pm 1$ ), and will receive a follow-up call on Day 42.

### **3.1.1.3 Dietary Requirements**

In the SAD phase, all healthy volunteers will receive either RO7049389 or placebo in the fasted state (overnight at least 8 hours). Subjects will not eat for at least 4 hours after the dose is administered. Lunch will be served approximately 4-5 hours post-morning-dose. In the MAD phase (*except cohort 4, which will be in the fasted state*), a standard breakfast or dinner will be served to healthy volunteers 30 minutes prior to dosing, which should be consumed within 30 minutes. RO7049389 or placebo will then be administered. Lunch will be served approximately 4-5 hours

**RO7049389—F. Hoffmann-La Roche Ltd**

30/Protocol YP39406, Version 4

post-morning-dose. An optional evening snack may be allowed provided that the fasting period is fulfilled before the next morning assessments.

Water will be allowed ad libitum until one hour prior to dosing and after one hour post dosing.

### **3.1.2 Dose-Escalation Decision Criteria**

A Safety Review of the data will be conducted by the Principal Investigator, the Medical Monitor, and the Sponsor Clinical Team prior to each RO7049389 dose-escalation.

Escalation to the next dose cohort will be based primarily on the safety and tolerability information (including adverse events [AEs], electrocardiograms [ECGs], vital signs, clinical laboratory test results) up to 48 hours post-dose (SAD), and secondarily on all available PK data up to 24 hours post-dose (SAD) in a minimum of 8 subjects (receiving active study drug or placebo) within the previous cohort. Doses will be escalated by three-fold increments but for higher doses the increments will be smaller than three-fold. The decision to escalate the dose will be made by mutual agreement between the Sponsor and the Investigator.

The MAD phase (Cohorts 2, 3, and 4) can begin after a washout period of at least one week, and once safety and tolerability information through 24 hours post-dose in the SAD phase (see [Figure 1](#)), and available safety and tolerability information from MAD cohorts in the entry-into-human study (YP39364) have been reviewed. Additionally, both the Sponsor and the Investigator must agree that the safety data can support continuing with the multiple-dose phase.

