## **4. MATERIALS AND METHODS**

### **4.1 STUDY POPULATION**

Due to the nature of this study, the actual number of subjects will be determined during the study. This study may require up to 76 subjects, including:

- About 40 healthy subjects to be enrolled in Cohort 1 of 4 subjects and Cohort 2 to Cohort 4 of about 12 subjects each.

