**RO7049389—F. Hoffmann-La Roche Ltd**

34/Protocol YP39406, Version 4

- Up to 36 healthy subjects to be enrolled if new subjects are needed for the MAD phase, in case of non-safety related discontinuations between two periods (i.e., replacement subjects),
- For each part, up to two back-up subjects can undergo the preparatory activities in order to replace participants who withdraw from the study for non-safety reasons.

Subjects who drop out of the study for non-safety reasons may be replaced to ensure sufficient data to characterize the safety and PK profile, and to make a dose-escalation decision. Subjects who withdraw from the study due to poor tolerability, or, due to study drug-related adverse events, will not be replaced.

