#### **4.5.2.3 Assessments at Study Completion/Early Termination Visit**

Study subjects who complete the study or discontinue from the study early will be asked to return to the clinic 7 days ( $\pm 1$  day) after the last dose of study drug for a follow-up visit and to complete assessments as specified in the SOA.

In case of early termination of a subject in SAD or MAD, a blood sample for PK assessment should be collected at the time of discontinuation.

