**RO7049389—F. Hoffmann-La Roche Ltd**

49/Protocol YP39406, Version 4

When a subject voluntarily withdraws from the study, or is withdrawn by the Investigator, samples collected until the date of withdrawal will be analyzed, unless subject specifically requests for these to be discarded or local laws require their immediate destruction.

Study subjects who withdraw from the study for safety reasons will not be replaced. Study subjects who withdraw from the study for other reasons will be replaced.

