## **6.1 DETERMINATION OF SAMPLE SIZE**

The sample size was determined by practical considerations and not based on statistical power calculations. Approximately four subjects will be enrolled in SAD cohort 1 (2 active treatment and 2 placebo). Approximately twelve subjects will be enrolled in each of the other SAD and MAD cohorts. They will be randomized to either active treatment (10 subjects per dose level) or placebo (2 subjects per dose level).

With ten subjects on active drug per dose group or cohort, there is a 94% chance to observe at least one AE that has an incidence rate of 25% in the population.

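### Cohort 1 (4 subjects, 2 active) cannot meet the 8-subject escalation minimum in 3.1.2 as planned, and its 2 active subjects cannot reach the count of 3 in the 3.1.2.1 stopping rule

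*Combined protocol and SAP*

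**What the plan says.** **Escalation gate.** Section 3.1.2 says that moving to the next dose cohort depends primarily on safety and tolerability up to 48 hours after the single dose, and secondarily on available PK data up to 24 hours, "in a minimum of 8 subjects (receiving active study drug or placebo) within the previous cohort". No cohort is exempted.

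**Cohort sizes.** Section 3.1.1: "Cohort 1 will include 4 healthy subjects, with 2 randomly assigned to RO7049389 and 2 assigned to placebo". Section 6.1 agrees: "Approximately four subjects will be enrolled in SAD cohort 1 (2 active treatment and 2 placebo". Section 4.1 gives the total: "About 40 healthy subjects to be enrolled in Cohort 1 of 4 subjects and Cohort 2 to Cohort 4 of about 12 subjects each". Cohorts 2 to 4 each have 10 active and 2 placebo subjects. Table 1 gives single doses of 200, 400, 600 and 800 mg for Cohorts 1 to 4.

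**The same decision described elsewhere.** The synopsis and 3.1.1 base escalation on safety and available PK data through 24 hours in the preceding cohorts. Neither names a minimum number of subjects.

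**Stopping rule.** Section 3.1.2.1 blocks escalation if, at any dose level, more than two active subjects have severe, clinically significant, related adverse events of the same character. Bullets on laboratory abnormalities and on vital-sign or ECG changes follow. Three provisions carry no count: one related serious adverse event halts dosing and escalation, Sponsor representatives review unblinded data before each escalation, and other findings can stop escalation at joint discretion whatever their incidence.

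**Replacement.** Section 4.1 allows that, for each part, "up to two back-up subjects can undergo the preparatory activities in order to replace participants" who leave for non-safety reasons. It adds: "Subjects who withdraw from the study due to poor tolerability, or, due to study drug-related adverse events, will not be replaced". Section 4.6.1.2 says that non-safety withdrawals will be replaced and sets no upper limit.

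**The concern.** Both rules govern how far healthy volunteers are exposed, in a study whose primary objective is safety. A gate that the planned cohort cannot pass leaves two courses at the first escalation: stop, or proceed against the protocol's own text. A count that the planned cohort cannot reach means that both active subjects at 200 mg could have severe, related events of the same character without triggering the predefined criterion. The decision would then rest on judgement alone. At stake are the clarity and the record of one escalation decision. No estimate or planned analysis is affected.

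**Working it through.** **Inputs.** Cohort 1: 4 subjects, 2 active (synopsis, 3.1.1, 4.1, 6.1). Cohorts 2 to 4: 12 each, 10 active (3.1.1). Escalation minimum: 8 (3.1.2). Smallest count that is more than two: 3 (3.1.2.1). Event rates for the stopping rule are not in the documents, so those below are assumptions. Subjects are treated as independent.

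**Reproducing the plan's own figures.**
- Enrolment: 4 + 3 × 12 = 40, as in 4.1. Adding the 36 possible replacements gives 40 + 36 = 76, also as stated. The cohort size of 4 is therefore built into the total and is not a slip in one section.
- Detection probability in 6.1: 1 − 0.75^10 = 0.9437, against the stated 94%. With Cohort 1's 2 active subjects, the same formula gives 1 − 0.75^2 = 0.4375.

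**Step 1: the escalation gate.**
- Planned 4 against required 8 is a shortfall of 4.
- The minimum is 8/12 = 67% of a later cohort but 8/4 = 200% of Cohort 1.
- If the 8 attaches only to the PK data, the comparison is still 4 against 8, and only the secondary input falls short.
- First-in-human data do not help, because the minimum is counted inside the preceding cohort of this study.
- The further 36 subjects (3 × 12) are for the MAD phase, which Cohort 1 does not enter.
- Dosing two back-ups as well gives 4 + 2 = 6, still under 8. Reaching 8 would take 8 − 4 = 4 non-safety withdrawals, each replaced, with the leavers' data also counted. That is not a plan.

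**Step 2: the count in the stopping rule.** Let X be the number of affected active subjects, binomial with n active subjects and event rate p.

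| Rule | n | p = 10% | p = 25% | p = 50% |
|---|---|---|---|---|
| X ≥ 3, later cohorts | 10 | 0.07 | 0.47 | 0.95 |
| X ≥ 3, Cohort 1 | 2 | 0 | 0 | 0 |
| X = 2, Cohort 1 | 2 | 0.01 | 0.06 | 0.25 |
| X ≥ 1, Cohort 1 | 2 | 0.19 | 0.44 | 0.75 |

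With 2 active subjects, P(X ≥ 3) is 0 even at p = 100%. A count of 3 is 3/10 = 30% of the active subjects in a later cohort and more than all of them in Cohort 1. The 200 mg q12h regimen cannot add to the count in time: it belongs to the Cohort 2 MAD phase, after the 400 mg single dose.

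**Step 3: a threshold of both active subjects.** The chance of a false stop is p²: 0.05² = 0.0025, 0.10² = 0.01, 0.25² = 0.0625.

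**The case against.** The strongest reply is that a small first cohort naturally falls outside a count rule, and that the plan does not lean on the count. One related serious adverse event stops dosing and escalation. Unblinded Sponsor review comes before each step, escalation needs agreement of Sponsor and Investigator, and the discretionary clause applies at any incidence. Two severe related events of the same character could be stopped under that clause today. Section 1.2.2 adds that the first-in-human study gave single doses of 150 to 2000 mg, and 200 and 400 mg twice daily for 14 days, all reported as well tolerated in a preliminary blinded review. The synopsis and 3.1.1 also state an escalation basis that Cohort 1 can meet.

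This all stands as to consequence, and it is why the point is minor. It does not waive the number in the section that sets the decision criteria, nor make a rule worded for any dose level work in a cohort of 2 active subjects. The looser wording in 3.1.1 and the synopsis shows that the sections disagree. It does not create an exception.

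A reader might infer four stronger things that the documents do not support:
- **That Cohort 1 has no stopping rule.** Only the count-based criterion is out of reach; the provisions above remain.
- **That 6 is a hard ceiling on Cohort 1 data.** Section 4.1 limits back-ups in preparation for each part, while 4.6.1.2 replaces non-safety withdrawals without a cap, and both 4.1 and 6.1 leave the exact number open. The firm comparison is the planned 4 against 8. A third active subject at 200 mg is likewise conceivable, through a non-safety replacement on active drug.
- **That laboratory, vital-sign and ECG changes certainly need 3 subjects too.** Those bullets probably sit under the count, but a page break intervenes and the nesting is unclear in the extracted text. Only the severe adverse event bullet is certain.
- **That a protocol deviation has already occurred.** The Version 4 rationale cites emerging data from this study, so Cohort 1 may well have escalated earlier. The version then in force is not available here.

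**Conclusion.** The point holds, at minor severity. The planned Cohort 1 falls 4 subjects short of the 8-subject minimum on either reading of 3.1.2, and it has 2 active subjects against the 3 that the severe adverse event criterion in 3.1.2.1 needs. The escalation basis is also described inconsistently between 3.1.2 and the synopsis and 3.1.1. The conclusion rests on the planned sizes and on the visible text of Version 4; Figure 1 is not reproduced in the copy read. It needs no assumed event rate, because the count is unreachable at every rate. Assumed rates enter only in describing the later cohorts and the suggested replacement threshold. The mismatch concerns the 200 to 400 mg step alone: Cohorts 2 and 3, with 12 subjects each, can satisfy both rules.

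**What to change.** **Section 3.1.2.** State that escalation from Cohort 1 requires review of data from all dosed Cohort 1 subjects (planned 4, both active subjects included). Keep the minimum of 8 for the 12-subject cohorts. For a subject who leaves and is not replaced, use data up to withdrawal. This is feasible: 4.6.1.2 says that "samples collected until the date of withdrawal will be analyzed", unless the subject asks for them to be discarded or local law requires destruction, and 4.5.2.3 says that on early termination "a blood sample for PK assessment should be collected at the time of discontinuation". Align the synopsis and 3.1.1 with this wording.

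**Section 3.1.2.1.** Set a Cohort 1 threshold that can be reached, for example both of the 2 active subjects affected by qualifying events of the same character. Leave a single case to the discretionary clause. State explicitly whether the laboratory and vital-sign or ECG bullets fall under the count.

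**If Cohort 1 has already escalated.** Record the data on which the decision was based. Whether it was a deviation depends on the version in force at the time.

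**Cost.** No additional subjects. The change is one of wording, but a change to a stopping rule may count as a substantial amendment needing IRB/EC and, where required locally, regulatory approval (9.5). Replacing a non-safety withdrawal in Cohort 1 means waiting for the replacement's data. The false-stop chance for a threshold of both active subjects is 0.0025 to 0.06 over assumed event rates of 5% to 25%.

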## **STUDY DESIGN**

### **Description of Study**

Healthy subjects will be enrolled into one of 3 planned cohorts and one optional cohort. Cohort 1 will include 4 healthy subjects, with 2 randomly assigned to RO7049389 (200mg) and 2 assigned to placebo. From Cohort 2 to Cohort 4, each of the cohorts will include 12 healthy subjects with 10 subjects randomly assigned to RO7049389 and 2 subjects randomly assigned to placebo.

In Cohort 1, subjects will receive one single dose of the assigned study medication. In subsequent cohorts, subjects will receive one single dose of the assigned study medication, followed by a wash out period of approximately 1-week before entering into a MAD phase of the study. Subjects in the MAD cohorts will be from the SAD cohorts after the wash out period, or from new enrollments if there are discontinuations between the SAD phase and MAD phase for reasons other than safety.

Escalation to the next single dose cohort will be based primarily on the safety and available PK data through 24 hours post single dose in the previous cohorts. The MAD phase may start after a wash out period of approximately 1-week, providing that the safety information through 24 hours post dose in the SAD phase at the same dose level, and available safety information from MAD cohorts in the entry-into-human study (YP39364), have been reviewed.

---

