**Figure 1 Overall Study Design and Dose-escalation**

Dotted lines indicate optional cohorts. See [Table 1](#) for additional information.

Escalation to the next single dose cohort will be based primarily on the safety and available PK data through 24 hours post-single dose in the previous cohorts. The MAD phase may start after a wash-out period of approximately 1-week, providing that the safety information through 24 hours post-dose in the SAD phase at the same cohort, and available safety information in the entry-into-human study (YP39364), have been reviewed.

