#### **SAD Phase**

RO7049389 or matching-placebo will be administered orally with 240 mL of water to the healthy subjects by investigational staff in the morning of Day 1 after an overnight fast of at least 8 hours.

Healthy volunteers will not eat for at least 4 hours after the dose is administered. Water will be allowed until one hour prior to dosing, and from one hour post-dosing. Approximately 4-5 hours after dosing, healthy subjects will be served lunch.

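### The condition for starting multiple dosing requires review of single-dose safety data only through 24 hours, although later data are collected before multiple dosing begins

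*Combined protocol and SAP*

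**What the plan says.** The condition for starting the multiple-dose (MAD) phase is stated three times, each time with a 24-hour window on the single-dose (SAD) data:

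- Synopsis, Description of Study: "providing that the safety information through 24 hours post dose in the SAD phase at the same dose level".
- Section 3.1.1, text under Figure 1: "providing that the safety information through 24 hours post-dose in the SAD phase at the same cohort".
- Section 3.1.2: "once safety and tolerability information through 24 hours post-dose in the SAD phase".

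All three also call for available safety information from the first-in-human study. Section 3.1.2 adds that "both the Sponsor and the Investigator must agree that the safety data can support continuing with the multiple-dose phase".

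On timing, the single dose is given "in the morning of Day 1 after an overnight fast of at least 8 hours" (Section 4.3.2.1), and subjects stay in the unit "for 3 nights from Day -1 through Day 2, and discharged on Day 3" (Section 3.1.1.1). The synopsis (Length of Study) lists ambulatory visits on Days 4, 5 and 8. MAD admission comes "after a post-SAD phase wash-out period of at least one week" (Section 3.1.1.2); the synopsis and 3.1.1 say approximately one week.

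For escalation to the next cohort, the preceding paragraph of 3.1.2 relies on adverse events, "electrocardiograms [ECGs], vital signs, clinical laboratory test results) up to 48 hours post-dose (SAD"), in at least 8 subjects of the previous cohort. The synopsis and 3.1.1 give 24 hours for that decision.

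**The concern.** Starting the MAD phase exposes a cohort to 14 days of dosing after a single dose. The data that must be reviewed first stop at 24 hours, about half of the in-clinic observation and half of the safety window that 3.1.2 uses for the next single-dose step. No reason for the shorter window appears in the supplied text, and the MAD sentence names no minimum number of subjects.

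At stake is a pattern of mild findings appearing after 24 hours in several subjects, such as non-serious adverse events or QTcF rises below the notification limit. Such a pattern would trigger none of the immediate-reporting rules and would lie outside the data that the review must cover. The plan collects later data but does not oblige anyone to look at them together before repeat dosing.

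**Working it through.** **The plan's own detection figure.** Section 6.1 gives a 94% chance of at least one case among 10 active subjects for an event with 25% incidence. Check: 1 − 0.75^10 = 0.944, which agrees. The figure carries no time window, and nothing below rests on it.

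**When the data exist.** Hours after a Day 1 morning dose are about (Day − 1) × 24.

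- Required window for MAD start: 24 h, i.e. Day 2.
- Discharge, Day 3: (3 − 1) × 24 = 48 h.
- Day 4: 72 h. Day 5: 96 h. Day 8: 168 h.
- Shortest reading of the wash-out, one week from the single dose: MAD Day 1 falls on SAD Day 8 and admission on SAD Day 7. The 48-hour point then precedes admission by 7 − 3 = 4 days for each subject, and the Day 4 and Day 5 visits precede it too.
- The synopsis (Length of Study) counts about one week of SAD treatment and then about one week of wash-out, which would place MAD start later still.

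**Dose step from SAD to MAD.** Projected MAD daily dose divided by SAD dose, from Table 1:

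| Cohort | Calculation | Ratio | MAD optional? |
|---|---|---|---|
| 2 | 2 × 200 / 400 | 1.00 | yes |
| 3 | 2 × 400 / 600 | 1.33 | no |
| 4 | 600 / 800 or 800 / 800 | 0.75 or 1.00 | yes |

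Only in Cohort 3 does the daily dose exceed the single dose, although each 400 mg administration is below 600 mg.

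**Subjects affected.** Cohort 3: 12 (10 active). If Cohorts 2 and 4 also run MAD: 3 × 12 = 36 (3 × 10 = 30 active).

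**Which provisions reach findings after 24 hours.**

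- Joint agreement (3.1.2): no time limit, but no later cutoff either; it follows directly on the 24-hour sentence.
- Limited re-screening before MAD (4.5.2.1): subject by subject.
- Investigator review of all ECG tracings (4.5.1.4), laboratory findings (5.2.5.4) and vital signs (5.2.5.5): no severity threshold, but subject by subject.
- Halt for a related serious event (3.1.2.1), notification of QTc above 500 msec or a rise above 60 msec (4.5.1.4), combined liver signals within 24 hours (5.1.3, 5.2.5.6): serious or threshold events only.
- Individual stopping rules (3.1.2.1): subject by subject.
- Safety Review (3.1.2, 4.2.1), unblinded internal review and cohort-level rules (3.1.2.1): cohort level, but tied to dose escalation. The text does not say that starting MAD counts as escalation.

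None of these expressly requires a cohort-level review of data after 24 hours before MAD starts.

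**The case against.** The strongest reply is that the gap opens only if the deciders ignore data they already hold. By the time of MAD the Investigator, one of the two parties who must agree, has had to review every ECG, laboratory result and vital sign, has sought adverse events at each contact (5.2.1), and will have re-screened the subjects. This is largely right. A reader might infer from the 24-hour wording that later findings go unseen, or that the deciders may not consider them. The documents do not support that: 24 hours is a floor, and the agreement clause is open-ended. What survives is that the listed duties are either subject-level or discretionary.

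A reader might also infer that 48 hours is the protocol's settled standard and that the MAD rule breaks it. That goes too far. The 48-hour window appears in 3.1.2 and in the ECG example of 3.1.2.1, while the synopsis and 3.1.1 use 24 hours for next-cohort escalation as well. MAD start is also a different decision, supported by a wash-out and first-in-human data. The comparison shows that 48 hours is workable and already treated as relevant; it does not show that 24 hours is an error.

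A third temptation is to combine the 94% of Section 6.1 with a share of late-onset events to quantify what would be missed. The documents give no onset times, and such a figure would treat the floor as the whole review.

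The clinical background also lowers the stakes. Cohort 3's regimen, 400 mg twice daily with food for 14 days, was well tolerated in the first-in-human study on preliminary blinded review (1.2.2), and dose and exposure may not exceed what that study evaluated (3.1.2.1). If Cohort 3's step counts as an escalation, the cohort-level reviews apply there too.

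**Conclusion.** The point holds as a low-severity improvement. The required review stops at 24 hours in all three statements of the rule, later data will be in hand before MAD, and no text obliges a cohort-level look at them. Later findings will usually be seen through the other provisions, so the residual risk is small. It matters most in Cohort 3 (12 subjects, 10 active), where the step is from 600 mg once to 800 mg per day; the most that could be affected is 36 subjects (30 active).

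This rests on Table 1's projected doses, which may be adjusted, and on the text as supplied. Figure 1 and the assessment schedules (Appendices 1 to 4) are not shown, so which tests fall between 24 and 48 hours cannot be confirmed. Section 3.1.1.1 mentions the Day 8 visit only for subjects not entering MAD, so the case rests mainly on the in-clinic stay to Day 3.

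**What to change.** In the synopsis, Section 3.1.1 and Section 3.1.2, replace the 24-hour condition with a requirement to review all SAD-phase safety and tolerability data available at the time of the MAD decision, and at least through 48 hours post-dose, for the subjects dosed in that cohort. This matches the safety window that 3.1.2 uses for escalation. The first-in-human data and the joint agreement stay as they are.

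The cost is wording in three places and slightly more review work, with no added visit or sample. If a cohort is dosed on one day, there is no delay, because the 48-hour point falls about four days before the earliest admission. The text does not say whether dosing is staggered. If it is, the last-dosed subject's data are needed to 48 rather than 24 hours, so the delay is at most about 48 − 24 = 24 hours, taking the current rule to cover every subject dosed in the cohort.
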